4.2. Protocol Deviations

Protocol deviations, including those related to COVID-19, will be defined in a separate document, including the process for major/minor classification.

All protocol deviations, COVID-19-related protocol deviations, and major protocol deviations will be summarized.

All demographic and baseline data for each patient will be provided in data listings. Medical history data, including baseline cardiac and ophthalmology history, prior surgeries/procedures, and pregnancy test results, will be presented in a data listing. Screening test results will also be presented in data listings.

4.4. Efficacy Evaluation

This Phase 3 study will use the APOLLO study as an external control. Patient-level data from this study will be compared with patient-level data from APOLLO for efficacy analyses.

Except for TTR endpoints, analysis models will include only the 2 treatment groups compared, vutrisiran and placebo (APOLLO), and only simple descriptives will be presented for patisiran (HELIOS-A). For TTR endpoints, vutrisiran and patisiran (HELIOS-A) will be compared unless otherwise specified.

For efficacy endpoints, 2-sided 95% confidence intervals and 2-sided nominal P values will be presented if applicable unless otherwise specified. Formal multiplicity-controlled hypothesis testing will be conducted as described in Section 1.3.1; all other P values presented will be considered descriptive.

4.4.1. General Efficacy Methods

Most continuous efficacy endpoints will be evaluated using an analysis of covariance (ANCOVA) model incorporating multiple imputation (MI) or a mixed-effects model for repeated measures (MMRM).

4.4.1.1. ANCOVA/MI

ANCOVA incorporating MI will be the default analysis for most continuous efficacy endpoints at Month 9.

MI is a broadly applicable technique for handling missing data. Missing data are imputed multiple times using a regression method. Each imputed data set is analyzed using the same analysis model, and the point estimates and standard errors are combined to provide inferences that reflect the uncertainty about the missing values. MI assumes the data are missing at random (MAR).

For a given endpoint, missing endpoint values will be multiply imputed separately for each treatment group using a regression procedure, with baseline information including baseline score and KPS as covariates and genotype, age at hATTR symptom onset, prior tetramer stabilizer use, region, FAP stage (I vs. II/III), Cardiac subpopulation, sex, and baseline NIS (<50 vs. ≥50) as factors. For NIS-related endpoints, the categorical baseline NIS score will not be included in the regression procedure.

One hundred imputed datasets (per treatment group) will be generated from the MI regression procedure using SAS PROC MI. Each of the imputed datasets will then be analyzed using an ANCOVA model, including a covariate (baseline value) and factors (treatment group; genotype; age of disease onset, baseline NIS score [<50 vs ≥ 50]), unless otherwise specified. For NIS-related endpoints, the categorical baseline NIS score will not be included in the model.

The resulting estimates (LS mean differences and standard errors) from the 100 imputed datasets will be combined using SAS PROC MIANALYZE to produce inferential results (difference in LS means, 95% CI for the difference, and the P value from the test that the difference is zero). [Rubin 1996] Combined LS mean estimates will be calculated as the average of the 100 complete-data estimates. A total variance estimate will be calculated as a weighted sum of within-imputation variance, which is the average of the complete-data variance estimates, and a between-imputation variance term. Complete details may be found in the SAS documentation for the MIANALYZE procedure (see Combining Inferences from Imputed Data Sets under Details: <http://support.sas.com/documentation/onlinedoc/stat/131/mianalyze.pdf>).

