4.4.1.2. MMRM

MMRM will be the default analysis for most continuous efficacy endpoints at Month 18. MMRM makes use of fully and partially observed data sequences from individual patients by estimating the covariance between data from different time points. The MMRM will be implemented using an unstructured approach to modeling both the treatment-by-time means and the (co)variances, leading to what is essentially a multivariate normal model wherein treatment group means at the primary time point are adjusted to reflect both the actually observed data and the projected outcomes from the patients with missing data. MMRM also assumes data are missing at random (MAR).

For most endpoints, the MMRM will include a covariate (baseline value), factors (treatment group; visit [Month 9; Month 18]; genotype; age of disease onset; baseline NIS score [<50 vs ≥ 50]), and an interaction term (treatment group by visit), unless otherwise specified. For NIS-related endpoints, the categorical baseline NIS score will not be included in the model.

LS mean and mean difference estimates, SEs, 95% CIs, and p-values at Month 9 and Month 18 will be presented.

An unstructured covariance structure will be used to model the within-patient errors. If the model fails to converge, the following covariance structures will be specified in sequence and the first to converge will be used:

1. Toeplitz
2. First order autoregressive
3. Compound symmetry

The Satterthwaite approximation will be used to estimate the degrees of freedom.

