4.4.2.2. Sensitivity Analysis: Propensity Score

To allow some control of more factors and covariates without saturating the model, a propensity score approach will be used to reduce the predictors to a single propensity score. The propensity score is defined as the probability of being treated with vutrisiran as obtained from a logistic

regression model of treatment group [vutrisiran; placebo (APOLLO)]. The logistic regression model will include the following baseline variables:

- Continuous variables
 - NT-proBNP (log-transformed)
 - mNIS+7
 - Norfolk QoL-DN total score
- Categorical variables
 - Previous tetramer stabilizer use (tafamidis/diflunisal) [Yes; No]
 - Karnofsky Performance Status (KPS) [60; 70-80; 90-100]
 - Cardiac Subpopulation [Yes; No]
 - PND score [I; II; IIIA; IIIB/IV]
 - Age at hATTR Symptom onset [< 50 ; ≥ 50]
 - Neuropathy Impairment Score (NIS) [< 50 ; ≥ 50]
 - Genotype [V30M; non-V30M]
 - FAP stage [I; II/III]

The primary endpoint will be analyzed in this sensitivity analysis using the [ANCOVA](#) method at Month 9 and [MMRM](#) method at Month 18, including the propensity score covariate in addition to the default model factors and covariates.

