4.4.4. Exploratory Efficacy Evaluations

The exploratory continuous endpoints, including change from baseline in NIS ([Section 9.1.1.2](#)), EQ-5D-5L index ([Section 9.1.3](#)), and EQ VAS, will be analyzed using an [ANCOVA/MI](#) model at Month 9, and using an [MMRM](#) at Month 18. For EQ-5D-5L, categorical descriptives for ordinal response within each EQ-5D domain will be presented at each visit.

The exploratory categorical endpoints, PND score, FAP stage, NYHA class, and KPS, will be descriptively summarized by presenting categorical descriptives for each visit. Categorical descriptives for patients with improving, no change, and worsening in PND/FAP at each postbaseline visit will also be summarized.

Cardiac structure and function will be assessed for all patients through echocardiograms. Cardiac stress and injury will be measured using serum levels of the cardiac biomarkers NT-proBNP,

troponin I, and troponin T. Quantification of these biomarkers will be performed at a central laboratory. Descriptive statistics will be provided for actual values, changes, and percentage changes from baseline in echocardiogram parameters and serum levels of troponin I, troponin T, and NT-proBNP by treatment group at each visit.

For the mITT Population and Cardiac Subpopulation, select echocardiographic parameters will be analyzed using an [MMRM](#) at Month 18 with covariate (baseline value), factors (treatment group; visit [Month 9; Month 18]), and an interaction term (treatment group by visit), including:

- Mean left ventricular (LV) wall thickness
- LV mass
- Global longitudinal strain
- LV end-diastolic volume
- Cardiac output

Cardiac biomarker NT-proBNP will be analyzed for the mITT population and Cardiac Subpopulation using an [ANCOVA/MI](#) model with covariate (baseline) and factor (treatment group) at Month 9. Additionally, NT-proBNP will be analyzed at Month 18 for the mITT population and Cardiac Subpopulation using an [MMRM](#) with covariate (baseline value), factors (treatment group; visit [Month 9; Month 18]), and an interaction term (treatment group by visit). A logarithmic transformation will be applied to both baseline and change from baseline values to normalize the data before fitting the MMRM. The adjusted geometric mean fold-change and the ratio of the fold-change (vutrisiran/placebo) from baseline will be presented.

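### The propensity-score analysis against the external placebo group omits sex and region, and the mITT cardiac models drop genotype and onset age

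*SAP*

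**What the plan says.** Section references are to the current SAP (Amendment 3) unless stated.

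- **Design (4.4).** "This Phase 3 study will use the APOLLO study as an external control". Patient-level vutrisiran data are compared with the placebo group of that trial.
- **Month 9 model (4.4.1.1).** The ANCOVA is specified as "including a covariate (baseline value) and factors (treatment group; genotype; age of disease onset" and, as a last factor, a two-level NIS category at baseline. Endpoints derived from the NIS lose that last factor, so mNIS+7 is adjusted for baseline score, genotype and onset age alone. Norfolk QoL-DN, 10-MWT, mBMI and R-ODS keep the NIS category.
- **Month 18 model (4.4.1.2).** "the MMRM will include a covariate (baseline value), factors (treatment group; visit [Month 9; Month 18]; genotype; age of disease onset", again with the NIS category except for NIS-related endpoints.
- **Imputation model (4.4.1.1).** Fitted separately in each treatment group, with a wider set of predictors: KPS and, among the factors, "prior tetramer stabilizer use, region, FAP stage (I vs. II/III), Cardiac subpopulation, sex".
- **Propensity score (4.4.2.2).** Introduced "To allow some control of more factors and covariates without saturating the model". The score is built from 11 baseline variables: log NT-proBNP, mNIS+7, Norfolk, prior stabilizer use, KPS, cardiac subpopulation, PND score, onset age, NIS category, genotype and FAP stage. It is added as a covariate to the ANCOVA without imputation at Month 9 and to the MMRM at Month 18. Section 4.4.3.1 extends it to Norfolk.
- **Subgroups (4.4.5).** The mNIS+7 and Norfolk effects are estimated within each sex and within each of three regions.
- **Cardiac endpoints (4.4.4).** The echocardiography MMRM, for both the mITT population and the Cardiac Subpopulation, is fitted "with covariate (baseline value), factors (treatment group; visit [Month 9; Month 18]), and an interaction term (treatment group by visit), including" five listed parameters. NT-proBNP is handled in the same reduced way, with only baseline and treatment group at Month 9.

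**The concern.** In a randomised comparison, leaving out a prognostic baseline variable costs precision. In an externally controlled comparison it can leave bias, because nothing makes the two groups alike on average. The propensity-score analysis is where this SAP looks for such bias, and its value depends on what the list contains.

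Sex and region are not stray candidates. The SAP treats both as worth having when it predicts missing outcomes and when it checks consistency of effect. Because imputation is done separately by group, both must already be available for the placebo patients. They are nevertheless absent from the one analysis meant to widen the adjustment. If the trials differ in sex or regional mix, and either relates to progression given the other covariates, the propensity-adjusted estimate could agree with the primary one while sharing the same bias.

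The cardiac models raise the same issue more simply. Genotype and onset age are adjusted for in every default model, yet the mITT echocardiography and NT-proBNP comparisons, which use the same external control, now do without them.

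**Working it through.** **1. Where sex and region enter a vutrisiran-placebo analysis**

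| Analysis | Sex | Region | Overall estimate adjusted? |
|---|---|---|---|
| ANCOVA/MI, comparison model | no | no | no |
| ANCOVA/MI, imputation model | yes | yes | no; affects imputed values only |
| MMRM | no | no | no |
| Propensity-score ANCOVA and MMRM | no | no | no |
| Subgroup analyses (mNIS+7, Norfolk) | conditioned on | conditioned on | no; one estimate per level |

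The Month 9 propensity analysis uses the ANCOVA without imputation, so there the two variables play no part at all.

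**2. Cardiac models**

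In SAP Amendment 2, Section 4.4.4, the mITT echocardiography and NT-proBNP analyses used the default models. The reduced model applied only to the Cardiac Subpopulation. The current Section 4.4.4 applies the reduced model to both populations, so genotype and onset age (and the NIS category) leave the mITT comparison. The amendment history gives only a general reason, to clarify and support the cardiac evaluation.

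**3. The plan's own power figure**

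Inputs from Section 1.4: about 160 patients at 3:1, so 160 × 3/4 = 120 on vutrisiran; mNIS+7 change 15 (SD 17) on placebo against 0; Norfolk 11.5 (SD 19.2) against -4; two-sided 0.05. The placebo number is not given, and a common SD is assumed. With a two-sample t-test, power exceeds 90% for mNIS+7 (difference 15) once the placebo group reaches 16, and for Norfolk (difference 15.5) once it reaches 19. The stated figure of more than 90% reproduces for any plausible placebo group.

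**4. Illustrative size of a bias in mNIS+7**

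Bias = imbalance in proportion × prognostic effect. Neither input is in the SAP, so these are assumptions:

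- 10 percentage points × 5 points = 0.5 points
- 20 percentage points × 10 points = 2 points, and 2/15 = 13% of the planned effect

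SE = 17 × √(1/120 + 1/n). With true difference zero and bias b, the rejection probability is Φ(-1.96 + b/SE) + Φ(-1.96 - b/SE).

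| Placebo n (assumed) | SE | Error, b = 2 | Error, b = 3 | Smallest significant difference |
|---|---|---|---|---|
| 40 | 3.10 | 9.9% | 16.2% | 6.13 |
| 60 | 2.69 | 11.5% | 20.0% | 5.30 |
| 80 | 2.45 | 12.9% | 23.1% | 4.84 |
| 100 | 2.30 | 14.0% | 25.6% | 4.54 |

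**5. Against the planned effect**

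For a true 15-point difference to lose significance, bias would have to remove 15 - 6.13 = 8.87 points at n = 40, or 15 - 4.54 = 10.46 at n = 100. A 2-point bias leaves 13.

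**6. Cost of adjustment**

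Sex takes 1 degree of freedom and region 2. In the propensity model these are spent before the outcome model, which still receives one score. Even if all 3 were taken from the outcome model, power is unchanged to the first decimal: mNIS+7 95.2% at n = 20 and 99.8% at n = 40; Norfolk 91.3% and 99.3%.

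**The case against.** **What stands against a wider criticism**

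- A reader might infer that all confirmatory placebo tests adjust for three variables only. They do not. The NIS category is retained in 6 of the 8 placebo steps of the US/Japan/Brazil hierarchy and 4 of the 5 in the EU one. Where it is dropped, for mNIS+7, the baseline score already contains NIS weakness and reflexes, 192 + 20 = 212 of the 244 NIS points.
- A reader might infer that sex and region are ignored. The subgroup analyses condition on each in turn for mNIS+7 and Norfolk, and Section 4.3 tabulates both by treatment group, so a gross imbalance would be seen.
- Use in an imputation model does not prove that a variable is prognostic after adjustment, or that it is imbalanced. Auxiliary variables are often included simply to make missing at random more plausible.
- A reader might infer that the Month 18 MMRM is weaker because it names fewer variables than the Month 9 imputation. It also conditions on the observed Month 9 outcome, and the pattern-mixture model in Section 4.4.2.3 examines departures from missing at random for mNIS+7 and, by cross-reference, Norfolk.
- Moving all the imputation covariates into the confirmatory models would be a debatable trade. The trial is open-label, placebo outcomes are already known, and a late change of primary covariates would invite the charge of data-driven modelling.
- The cardiac analyses are exploratory, with descriptive p-values.

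**What it does not answer**

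Subgroup estimates are not an overall adjusted estimate, and a baseline table shows imbalance without correcting for it. The aim of not saturating the model explains the use of a score, but it is no reason to leave sex and region out of that score.

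**Conclusion.** The point holds as a gap in the sensitivity analysis and in the mITT cardiac models, and as a cheap improvement. No overall vutrisiran-placebo estimate is adjusted for sex or region, although both are collected and used elsewhere in the SAP. The mITT echocardiography and NT-proBNP comparisons lack genotype and onset age, which the default models include.

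The SAP does not support the stronger conclusion that the primary result is confounded. It gives no sex or region distribution and no prognostic effect for either, so the size and even the direction of any bias are unknown. The error rates of about 10-14% for 2 points of bias rest on an assumed imbalance, an assumed prognostic effect, an assumed 40-100 placebo patients and a common SD of 17. They describe a true null. Under the planned 15-point mNIS+7 effect, roughly 9 to 10 points of bias would be needed to lose significance. Section 1.4 gives no planned effect for 10-MWT, mBMI or R-ODS, so no such margin can be stated for them.

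**What to change.** 1. In Section 4.4.2.2, add sex and region (North America; Western Europe; Rest of World) to the categorical variables of the propensity model. If Month 9 results are already known, label the revised Month 9 analysis as added afterwards and prespecify it for Month 18.
2. In Section 4.4.4, restore genotype and age at onset in the mITT echocardiography and NT-proBNP models. The reduced model can stay for the smaller Cardiac Subpopulation.
3. Leave the confirmatory ANCOVA and MMRM unchanged. A version with the full imputation covariate set may be added, as a supportive analysis only.

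Cost: SAP wording, 3 degrees of freedom in a slightly larger propensity model, and 2 in the mITT cardiac models (genotype and onset age, each with two levels). No new data are needed. If a region is sparse in either trial, the propensity model may fit poorly; the rule in Section 4.4.5 for regrouping regions with fewer than 20 patients could be applied here too.

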4.4.1.2. MMRM

MMRM will be the default analysis for most continuous efficacy endpoints at Month 18. MMRM makes use of fully and partially observed data sequences from individual patients by estimating the covariance between data from different time points. The MMRM will be implemented using an unstructured approach to modeling both the treatment-by-time means and the (co)variances, leading to what is essentially a multivariate normal model wherein treatment group means at the primary time point are adjusted to reflect both the actually observed data and the projected outcomes from the patients with missing data. MMRM also assumes data are missing at random (MAR).

For most endpoints, the MMRM will include a covariate (baseline value), factors (treatment group; visit [Month 9; Month 18]; genotype; age of disease onset; baseline NIS score [<50 vs ≥ 50]), and an interaction term (treatment group by visit), unless otherwise specified. For NIS-related endpoints, the categorical baseline NIS score will not be included in the model.

LS mean and mean difference estimates, SEs, 95% CIs, and p-values at Month 9 and Month 18 will be presented.

An unstructured covariance structure will be used to model the within-patient errors. If the model fails to converge, the following covariance structures will be specified in sequence and the first to converge will be used:

1. Toeplitz
2. First order autoregressive
3. Compound symmetry

The Satterthwaite approximation will be used to estimate the degrees of freedom.

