1.3.2. Multiple Comparisons Procedure (EU/Other Regions)

In the EU, during its scientific advice procedure, the EMA/CHMP/SAWP indicated a preference for a marketing authorization application based upon 18 months data. Therefore, the Month 9 endpoints included in the US/Japan/Brazil multiple comparisons procedure (MCP) will not be included in the MCP for the EU and other regions, where instead mNIS+7 change from baseline at Month 18 will be considered the primary endpoint. The overall familywise error rate in the EU and other regions will be controlled at $\alpha=0.05$ for the primary and secondary endpoint hypothesis tests as follows:

Table 2: Multiple Comparisons Procedure (EU/Other Regions)

MCP Step ^a	Endpoint	Comparison group vs Vutrisiran	MCP Criteria
Evaluated at the Month 18 analysis timepoint			
1	Modified Neuropathy Impairment Score +7 (mNIS+7) change from baseline at Month 18	Placebo (APOLLO)	Nominal P value $\leq \alpha$
2	Norfolk Quality of Life-Diabetic Neuropathy (Norfolk QoL-DN) total score change from baseline at Month 18	Placebo (APOLLO)	Nominal P value $\leq \alpha$

MCP Step ^a	Endpoint	Comparison group vs Vutrisiran	MCP Criteria
3	10-MWT gait speed change from baseline at Month 18	Placebo (APOLLO)	Nominal P value $\leq \alpha$
4	mBMI (BMI [kg/m ²] multiplied by serum albumin level [g/L]) change from baseline at Month 18	Placebo (APOLLO)	Nominal P value $\leq \alpha$
5	R-ODS change from baseline at Month 18	Placebo (APOLLO)	Nominal P value $\leq \alpha$
6	TTR percent reduction through Month 18	Patisiran (HELIOS-A)	2-sided 95% LCB for treatment difference $> -10\%$

^a Per serial gatekeeping MCP, if the MCP criterion is satisfied in a given step, the hypothesis test is deemed statistically significant and the next step will be evaluated; otherwise all hypotheses in the given and subsequent steps are deemed not statistically significant.

LCB=lower confidence bound; MCP=multiple comparisons procedure.

For filings in the EU and other regions, results for the primary endpoint, mNIS+7 change from baseline at Month 18, must be statistically significant to declare a positive trial.

References to the primary and secondary endpoints in the remainder of this document refer to those endpoints defined in the study objectives and endpoints (Section 1.2), corresponding to the US/Japan/Brazil MCP (Section 1.3.1).

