4.4.2. Primary Efficacy Evaluations

The primary endpoint is change from baseline at Month 9 for mNIS+7 (Section 9.1.1). The primary comparison will be conducted at Month 9. The primary endpoint will be analyzed using the general ANCOVA/MI methods.

Additionally, change from baseline at Month 18 for mNIS+7 will be analyzed as a secondary endpoint using the general MMRM methods.

4.4.2.1. Sensitivity Analysis: Including Data Post Local Standard Treatment for hATTR amyloidosis or Post Serious COVID-19 AE

The primary analysis will not include assessments performed after the initiation of local standard treatment for hATTR amyloidosis or on or after onset of a serious COVID-19 AE (Section 3.5). Sensitivity analysis of mNIS+7 change from baseline including data post local standard treatment for hATTR amyloidosis or post serious COVID-19 AE from either study will be conducted using the ANCOVA method at Month 9 and MMRM method at Month 18.

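### The default Month 18 MMRM shares one baseline slope between Months 9 and 18, so adjustment against the external placebo group may be incomplete at Month 18

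*SAP*

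**What the plan says.** All references are to SAP Amendment 3.

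- Section 4.4.1.2 gives the Month 18 model a baseline covariate and "factors (treatment group; visit [Month 9; Month 18]; genotype; age of disease onset", plus a categorical NIS term that is dropped for NIS-related endpoints. It closes the list of terms with "and an interaction term (treatment group by visit), unless otherwise specified" and names no other interaction.
- The same section states: "An unstructured covariance structure will be used to model the within-patient errors". It describes the model as an "unstructured approach to modeling both the treatment-by-time means and the (co)variances".
- Section 1.3.2, for the EU and other regions: "mNIS+7 change from baseline at Month 18 will be considered the primary endpoint". Section 4.4.2 sends that endpoint to this model: "change from baseline at Month 18 for mNIS+7 will be analyzed as a secondary endpoint using the general MMRM methods".
- Section 4.4: "This Phase 3 study will use the APOLLO study as an external control".
- Section 4.4.2.2 (propensity score) adds the score as one more covariate to the default model, without a visit interaction.
- Section 4.4.2.3 and Table 4 plan a Month 18 pattern-mixture analysis with a modified ANCOVA/MI, which is a single-visit model.

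No section adds baseline by visit for mNIS+7.

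**The concern.** In a randomised comparison a shared baseline slope does little harm, because the groups have the same expected baseline and the slope multiplies a difference close to zero. Here the two groups come from different trials, so covariate adjustment has to do what randomisation would otherwise do. If *NIS-related* includes mNIS+7, as it appears to, the categorical NIS term drops out. The single baseline coefficient is then the only direct measure of neuropathy severity in the EU primary model.

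The Month 9 ANCOVA fits a slope specific to Month 9. The Month 18 model does not fit one specific to Month 18, and the plan gives no reason for the difference. The same model serves the Month 18 placebo comparisons in both testing hierarchies: steps 1 to 5 for the EU and other regions, and steps 4 to 8 for US/Japan/Brazil. At stake is whether the reported Month 18 difference and its interval are fully adjusted for baseline.

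**Working it through.** **Inputs from the SAP (Section 1.4).** About 160 patients at 3:1, so about 120 on vutrisiran. Placebo mNIS+7 change at Month 9 is 15 with SD 17, against an assumed 0 on vutrisiran. Norfolk change is 11.5 with SD 19.2, against -4. Alpha is 0.05, two-sided.

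**Not in the SAP, so assumed.** The Month 18 SD, the Month 9/18 correlation, the baseline slopes, the baseline difference between groups, and the placebo sample size.

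**1. The plan's own figure.** With 120 on vutrisiran, a two-sample t-test exceeds 90% power for mNIS+7 (difference 15, SD 17) from 16 placebo patients, and for Norfolk (difference 15.5, SD 19.2) from 19. The stated power of more than 90% reproduces. It concerns Month 9 only.

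**2. Weight of the Month 9 slope.** Let k = SD at Month 18 / SD at Month 9, and let rho be the residual correlation. With complete data, free treatment-by-visit means and unstructured covariance, the shared slope is w9·b9 + (1 - w9)·b18, where

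w9 = (k² - rho·k) / (1 + k² - 2·rho·k).

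| k | rho 0.5 | rho 0.7 | rho 0.8 |
|---|---|---|---|
| 1.0 | 0.50 | 0.50 | 0.50 |
| 1.2 | 0.68 | 0.79 | 0.92 |
| 1.35 | 0.78 | 0.94 | 1.12 |
| 1.5 | 0.86 | 1.04 | 1.24 |
| 2.0 | 1.00 | 1.18 | 1.33 |

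For example, at k = 1.35 and rho = 0.7: (1.8225 - 0.945) / (2.8225 - 1.89) = 0.8775 / 0.9325 = 0.94. The weight reaches 1 when rho = 1/k. The fallback structures in Section 4.4.1.2, in their standard forms, impose equal variances. They would set the weight at 0.50, so the adjustment would also depend on whether the unstructured model converged.

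**3. Residual bias at Month 18.** The model subtracts shared slope × D, where D is the baseline difference. Full adjustment would subtract b18 × D. The error is (b18 - shared slope) × D = w9 × (b18 - b9) × D.

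| b18 - b9 | D | w9 = 0.5 | w9 = 1.0 |
|---|---|---|---|
| 0 | any | 0 | 0 |
| any | 0 | 0 | 0 |
| 0.05 | 5 | 0.12 | 0.25 |
| 0.10 | 10 | 0.50 | 1.0 |
| 0.20 | 15 | 1.5 | 3.0 |

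Weights above 1 raise these in proportion: the last row becomes 3.3 at w9 = 1.1.

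**4. Check by simulation.** 80 placebo and 120 vutrisiran patients, SD 17 at Month 9, k = 1.5, rho = 0.7, b9 = 0.05, vutrisiran less severe at baseline by D, 30% and 9% missing at Month 18, 400 replicates (Monte Carlo SE about 0.2). Negative values favour vutrisiran.

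| D | b18 | Bias, planned model | Bias with baseline × visit | Difference | Formula, w9 = 1.04 |
|---|---|---|---|---|---|
| 10 | 0.10 | -0.72 | -0.19 | -0.53 | 0.52 |
| 10 | 0.20 | -1.43 | 0.08 | -1.51 | 1.56 |
| 15 | 0.10 | -1.04 | -0.30 | -0.74 | 0.78 |
| 15 | 0.20 | -2.51 | -0.27 | -2.24 | 2.34 |

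With equal slopes, or with D = 0, the planned model showed no bias beyond Monte Carlo error. The SE of the Month 18 difference was 3.8 to 4.2. In a second simulation, with SDs 17 and 26 and rho 0.7, it was about 3.9 with or without the interaction.

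**5. Meaning for the interval.** With SE 4, a bias of 1 point is 0.25 SE. Coverage of a 95% interval is then about Φ(1.71) - Φ(-2.21) = 94%. A bias of 3 points is 0.75 SE, and coverage is Φ(1.21) - Φ(-2.71) = 88%.

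**The case against.** The strongest reply is that the model is explicit, can be programmed as written and is not contradicted elsewhere, so this is a refinement and not a demonstrated error. That stands. So do these points:

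- A reader might infer that the shared slope comes almost wholly from Month 9. The SAP gives neither the Month 18 SD nor the correlation, and the weight runs from 0.50 to above 1.
- A reader might infer that the EU comparison is biased, or biased in favour of vutrisiran. The SAP shows neither a baseline difference nor a changing slope. If either is zero the bias is zero, and the opposite imbalance would work against vutrisiran. Nor does the SAP show that slopes must grow with time: mNIS+7 has a ceiling of 304, and walk speed has a floor of 0.
- Section 4.4.1.2 claims an unstructured form only for treatment-by-time means and covariances. It makes no such claim for covariate slopes, so it does not contradict itself.
- The sizes above are for mNIS+7. The SAP has no inputs that would give a size for Month 18 Norfolk, 10-MWT, mBMI or R-ODS.
- The Month 18 pattern-mixture analysis fits its own Month 18 slope and is a partial check. It also changes the missing-data assumptions, so a difference from the MMRM could not be traced to the slope.

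None of this supplies a reason to leave the term out. The propensity-score MMRM does not cure the problem, because it is built on the same default model.

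**Conclusion.** The point holds as a conditional one. Because the control is external, the default Month 18 MMRM may adjust incompletely for a baseline difference when the baseline slope changes between visits. For mNIS+7 the residual bias is about 0 to 3 points, in either direction, against an SE of about 4. This assumes baseline differences up to 15 points, slope changes up to 0.20 and a Month 9 weight up to about 1. At most that is about three quarters of a standard error, and one fifth of the 15-point difference planned at Month 9 (3/15). It can shift the estimate and reduce interval coverage, but it is unlikely to change the mNIS+7 superiority decision. The same reassurance cannot be given in figures for the other Month 18 endpoints, because the SAP states no expected Month 18 effects for them.

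**What to change.** In Section 4.4.1.2, add baseline value by visit to the default MMRM beside treatment group by visit. The change carries into the propensity-adjusted MMRM (Section 4.4.2.2) and the component/domain MMRMs (Section 4.4.6), which are built on the default model.

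Genotype by visit and age at onset by visit are optional, and in the default model only. The subgroup MMRMs (Section 4.4.5) have their own shorter list of terms. Age at onset is not in them, and genotype is not in the genotype-subgroup models, so no interaction should be added there without its main effect.

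The cost is one line of text, the matching model code and about one degree of freedom, with essentially no change in the standard error. If the slopes turn out equal, almost nothing is lost.
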